10.0 DESIGN CONSIDERATIONS

The PROUD study was designed to be generalizable to diverse healthcare systems and to inform health system leaders on how implementing the MA Model might increase OUD treatment and decrease acute care utilization in “real world” settings. The design has a number of strengths. First, we recruited a pair of PC clinics from diverse health systems: safety net clinics (MF and HH); an academic clinic (UM); integrated delivery systems with health care delivery and health insurance combined in a single organization (HF and KPWA); and a regional healthcare delivery system (MC). Moreover, these systems are geographically diverse and we will use secondary data to evaluate outcomes in a generalizable sample of patients aged 16 to 90 years old. Second, all 6 health care systems agreed to implement the MA Model in a randomly selected clinic, out of a pair of clinics they provided. Third, all systems have a demonstrated ability to provide data on buprenorphine and injectable naltrexone orders or dispensed medications, all diagnoses, and all health care utilization in their health care system. At the same time, the design also has limitations; we address major limitations below.

10.1 Design Considerations: Intervention and Control

10.1.1 Choice of the Intervention

Although the MA Model has an outstanding track record of engaging and retaining PC patients in OUD treatment, dissemination of the MA Model could be hampered by several factors. First, it requires a large upfront investment in a fulltime NCM, and there are often regional shortages of nurses, which might make hiring difficult in some locations, especially with the required skills and openness to treating OUDs. Ideally, we could have tested a more flexible, lower cost model as well. However, that was not feasible for budgetary reasons. ***To address this limitation we will compare the MA Model to 10 other exemplar clinics in secondary observational analyses described below in Section 11.3.3.***

10.1.2 Usual Care Controls

Use of a usual care control has a number of strengths for this study, as outlined above, but also poses a number of challenges.¹⁴⁰ These include diversity of UPC across sites and clinics at baseline and over time, and the challenge of defining what usual care includes at each site. We address these with robust assessment at baseline and during the study by monitoring OUD care in all clinics with qualitative and quantitative data. Qualitative data to be collected might include new leadership or behavioral health clinicians in PC, or changes in requirements for prior authorization of injectable naltrexone, and whether or not care management for mental health or substance use disorders is available in a UPC or intervention clinic. Quantitative data to be collected include the number of PC providers total, number of PC providers who prescribe buprenorphine, number of integrated behavioral health clinicians, and movement of providers between clinics (PROUD, UPC, and non-randomized UPC). At the same time we avoid any contact between the investigators and PROUD Intervention or UPC clinic staff, and the site lead investigator and project manager will only check in with 1-2 key stakeholders quarterly about changes in usual care over time, to avoid contamination of the UPC clinics and to increase generalizability.

10.2 Design Considerations Regarding Study Samples

10.2.1 Recruited Clinics Are Not “Usual”

During site engagement in Phase 1, most clinics could not participate due to leadership at some level not wanting to treat OUDs in PC (i.e., leaders at the highest level of the organization, regional leadership, addictions leadership, PC leadership or clinic leadership) or the absence of 3

clinicians willing to prescribe buprenorphine. Thus, UPCs in the trial are not typical. To address this we have asked all sites to provide data on 4 non-randomized PC clinics and five sites have said they are able to do so. We will also ask 2 other health systems providing exemplar PC clinics, to also provide 4 UPC clinics. Secondary analyses comparing the 12 PROUD trial clinics to these other usual care clinics prior to baseline, and comparing outcomes in the randomized UPC clinics and in these non-randomized UPC clinics, will inform generalizability of the results of the trial to other settings.

10.2.2 Imbalance in the Size of the Two Randomized Clinics at Each Site

Imbalance in the size and other characteristics of the 2 clinics at each site could bias the study. The NCM being hired through the PROUD intervention has a finite capacity to treat approximately 100-125 total patients based on experience in MA. Because our main outcome is reported per 10,000 patients in the clinic pre-randomization, if 2 clinics each treated 100 patients for OUD, but one saw 20,000 total patients and the other saw 10,000 total patients in the year prior to randomization, the patients per 10,000 treated per clinic would be 50 or 100, respectively. However, none of the clinics has more than a 2-fold difference in size and we hypothesize a 5-10 fold increase in days of buprenorphine treatment (reflecting the number of patients who initiate as well as improved retention of patients in treatment). Therefore, the relatively small imbalance is thought acceptable.

10.2.3 Possible Cross-over Between UPC to Intervention Clinics

Although cross-over between the two clinics was less than 0.5% at all sites in 2016 based on Phase 1 data, it is still possible that this could change when patients with OUDs want buprenorphine: they might travel to the PROUD intervention clinic to obtain it. Main analyses could be biased to the null if patients from UPC sought OUD treatment in the PROUD intervention clinic. We will therefore measure crossover at baseline and throughout the trial, will report crossover in our main manuscript, and will conduct sensitivity analyses to address crossover as described below (Section 11.7.1.3).

10.3 Design Considerations Regarding Measures

10.3.1 Primary Outcome Measure for the Primary Objective

Treatment of OUDs for at least a year has been associated with decreased acute care utilization.³⁶ We had therefore initially hoped to use OUD medication treatment for at least a year as our primary outcome. However, preliminary simulations by the DSC early in Phase 1 revealed that 6 sites would be inadequate for such a trial, and we did not have adequate budget to conduct an adequately sized trial for that dichotomous outcome. However, we developed a novel scaled measure of “patient-days of OUD treatment” that reflects both initiation and retention in treatment with medication treatment for OUDs. We will conduct preliminary analyses of this outcome, which is complicated to model by the fact that it is zero for most patients.

10.3.2 No Data on Methadone Maintenance OTP for Most Sites

It is possible that availability of PC treatment of OUDs could shift patients from OTPs into PC, in contrast to initiating new patients into OUD treatment. Also, the MA Model is expected to increase treatment in OTPs because some patients seeking buprenorphine will not be appropriate candidates for PC management or they will need to transfer to more structured programs. Ideally, we would therefore have OTP data from all sites. However, that was not possible: we could only obtain claims for methadone OTPs for all patients at one site (KPW) and 30% of patients at another (HF). Another site (MF) had one internal OTP program. However, even when OTP claims were available, estimating our outcome “days of OUD treatment” from the claims required a large

number of assumptions. Therefore, a decision was made to use only evidence-based medication treatments provided in medical settings (buprenorphine and injectable extended-release naltrexone) in calculating days of OUD treatment. Nevertheless, to address the limitation of not having a measure of days treated with methadone from OTPs for all sites, we will conduct analyses using the available methadone maintenance data from 3 sites to evaluate whether implementation of the MA Model impacts utilization of methadone (in addition to buprenorphine and injectable naltrexone), and whether including OTP data changes our main results.

10.3.3 Timing of Outcomes Measurement

Initially, we planned to start measurement 6 months after randomization to allow sites up to 6 months to hire the NCM before outcome measurement began. However, several stakeholders pointed out that leaders of health systems would be interested in information on outcomes beginning at the time a decision was made to hire an OBAT NCM, which occurs at randomization in this trial. As a result, based on discussions with the protocol development team, a decision was made to measure outcomes starting at randomization. Process measures will include timing of NCMs and prescribers starting to care for patients with OUDs.

10.3.4 Use of EHR Orders for Buprenorphine and Injectable Naltrexone

Most sites in the PROUD trial do not provide us with data on dispensed medications but instead provide EHR prescription orders. Orders could have been written and never dispensed. However, we expect that is uncommon for buprenorphine. We will address this limitation by conducting sensitivity analyses with the outcome restricted to episodes of OUD treatment with at least a series of two orders (suggesting that the patient picked up and used the first prescription). We will also use data from the two sites that are health plans, which can therefore provide dispensed medications (KPWA and HF), to conduct sensitivity analyses to see if use of dispensed medications (compared to medication orders) changes main results at those two sites.

10.3.5 Incomplete Ascertainment of Acute Care and Other Patient Outcomes

Most participating sites are not health insurance plans (which typically have quite complete ascertainment of health utilization outcomes on their enrolled samples). Although it appears from preliminary Phase 1 analyses that we are capturing large and somewhat comparable amounts of acute care in all sites, it is possible that the two randomized clinics in a health system could differ in their ascertainment of acute care outcomes. For example, one of the clinics might be near an “internal” hospital or ED from which data are captured, while another of the clinics might be near another hospital or ED that is not part of their delivery system. This could create biased ascertainment of outcomes. To address this, we will qualitatively describe usual PC in both clinics at baseline including all nearby acute care facilities and distance to each clinic, and evaluate for differential acute care use pre-randomization to understand the extent to which this might impact secondary outcomes.

10.3.6 Incomplete Death Data

Most sites participating are not health insurance plans and do not have population based death data (i.e., from state vital status files). Relying on the EHR could bias the study towards greater ascertainment of OUD deaths in the PROUD intervention clinics due to NCM documentation. Mortality rates in patients with OUDs documented in EHRs are high (48.6 per 1000 person-years or a 10-fold increase over expected death rates (standardized mortality ratio of 10.3 (95% confidence interval [CI] 9.4–11.3)).³⁰ We address this below with sensitivity analyses and with an ancillary study to evaluate the intervention’s impact on death among patients with OUDs.

11.0 STATISTICAL ANALYSIS

11.1 Overview of Primary and Secondary Outcomes (Endpoints)

The planned primary outcome is a continuous measure defined as the total count of patient days of OUD treatment during the 2-year follow-up period per 10,000 patients seen in the clinic during that period. This outcome reflects the success of implementation of high quality OUD treatment in PC, including recognition of OUD (both previously diagnosed and newly diagnosed patients), as well as initiation of OUD treatment with medications and persistence of medication treatment, reflecting retention in OUD care. The study sample for calculating the number of patient days of OUD treatment is defined as all clinic patients who had a PC visit at any time in the 3 years prior to randomization or in the 2 years of follow-up after randomization. For each clinic, the primary outcome measure is operationalized as the total number of patient days covered by OUD treatment in the 2 years of follow-up divided by the number of patients in the clinic during that time and then multiplied by 10,000. Only buprenorphine and injectable naltrexone are considered OUD treatment when calculating the primary outcome measure.

Our hypothesis is that the PROUD intervention, compared to usual PC, will be associated with an increase in the number of patient days of medication treatment for OUDs during the 2 years after randomization. In addition to testing whether that is true when the MA Model is implemented in the diverse health systems in this trial, the analyses described below also estimate the magnitude of the increase.

As above, the secondary outcome is days of acute care utilization including visits to urgent care clinics, visits to EDs and days hospitalized after randomization among patients with or at increased risk for an OUD diagnosis in the 3 years before randomization. This is a patient outcome and reflects health benefits of the PROUD intervention to patients.

Our hypothesis is that the PROUD intervention, compared to usual PC, will be associated with a decrease in days of acute care utilization during 2 years of follow-up by PC patients diagnosed with OUDs in the 3 years prior to randomization.

11.2 Statistical Methods for Primary and Secondary Outcomes

11.2.1 Statistical Methods for the Primary Outcome

Since randomization and the intervention occur at the clinic-level, the unit of analysis will be clinic and not patient for the primary outcome. The mixed effects model evaluating the effect of the PROUD intervention is:

$$y_{ij} = \alpha + \beta * trt_{ij} + \gamma * z_{ij} + \theta_j + \epsilon_{ij}$$

where

- y_{ij} is the observed value of the primary outcome measure (see Section 8.1) for clinic i at site j
- trt_{ij} is the treatment indicator (PROUD intervention) for clinic i at site j
- z_{ij} is the observed value of the primary outcome measure for the two years prior to randomization (hereafter baseline) for clinic i at site j
- θ_j is the random effect for site j and is distributed $N(0, \sigma_\theta^2)$
- ϵ_{ij} is the error term for clinic i in site j and is distributed $N(0, \sigma_\epsilon^2)$

The research question of interest is whether β significantly exceeded zero at the 0.05 level, thus a one-sided hypothesis test. Example SAS code for the analysis is as follows:

```
proc mixed data = primout;  
  
  class arm;  
  
  model scaletotdays = arm basevalue / solution;  
  
  random intercept / subject = site;  
  
  estimate "Treatment Effect" arm 1 -1;  
  
run;
```

where “arm” is the treatment assignment, “scaletotdays” is the value of the primary outcome measure, “basevalue” is the value of the primary outcome measure for the two years prior to randomization and “site” indexes the different health care systems.

This model allows for clinics to be correlated within a health care system, in addition to allowing for an association of the scaled days of OUD treatment prior to randomization with the post-randomization outcome. The latter relationship is assumed to be linear. Secondary analyses of the primary outcome may relax this assumption by considering alternative relationships, such as inclusion of a quadratic term. Further, the need for a random effect of health care system can be evaluated by testing whether the variance of that term (i.e., σ_{θ}^2) is zero.

11.2.2 Statistical Methods: Secondary Outcome - Acute Care Utilization

Detailed analytic specifications for the secondary outcomes identified in Section 8.2 will be developed during start-up and detailed in a separate SAP. Below are brief descriptions of the proposed approaches.

We will evaluate, among individuals who have an OUD diagnosis, whether acute care utilization differs among patients from PROUD intervention clinics as compared to patients from UPC clinics (acute care utilization defined above in Measures Section 8.2). Our primary analysis will focus on patients who were identified as having an OUD prior to randomization. Because the PROUD intervention is expected to increase diagnosis of OUD, those patients diagnosed post-randomization in the PROUD intervention clinic are likely to be different than those diagnosed prior to implementation, and could therefore lead to biased estimates of the treatment effect if included in the analysis. Our current plan will be to exclude those diagnosed with OUD after randomization from the primary Objective 2 analysis. Secondary Objective 2 analyses (described below) will include those individuals who were not identified until post-randomization and will incorporate analytic methods for observational data.

11.2.2.1 Primary Analysis of Objective 2

We hypothesize that, among patients who had a PC visit and were identified (pre-randomization) as having an OUD diagnosis (documented in their EHRs in the 3 years prior to randomization), individuals from a PROUD intervention clinic will have decreased acute care utilization after randomization as compared to individuals from a UPC clinic. We plan to fit a mixed-effect Poisson regression model (with log link) at the patient level to the number of days of acute care utilization. The model will account for clustering of patients within a clinic by including clinic-specific random intercepts. Specifically, the regression model will be of the following form:

$$\log[E(y_{ijk})] = \alpha + \beta * trt_{ij} + \gamma * z_{ijk} + \theta_{ij}$$

where

- y_{ijk} is the observed number of days of acute care utilization of patient k in clinic i of site j
- trt_{ij} is the treatment indicator (PROUD intervention) for clinic i in site j
- z_{ijk} is a vector of clinic and/or patient-level covariates
- θ_{ij} is the random effect for clinic i in site j

We plan to adjust for a parsimonious list of pre-specified, baseline covariates that are known to be strongly associated with the outcome from the literature such as age, gender, race/ethnicity at baseline,⁷³ comorbidity and utilization prior to randomization, to be specified in the stand-alone SAP. We will evaluate our primary Objective 2 hypothesis by testing the null hypothesis $H_0: \beta = 0$ versus the two-sided alternative hypothesis that β is non-zero with a type 1 error rate of 0.05. As a sensitivity analysis, we will consider also including in the model any additional covariates found to differ between individuals with a prior OUD diagnosis in the PROUD intervention clinics as compared to the UPC clinics pre-randomization, as well as patient-level variables found to be associated with acute care utilization among patients with OUDs.

11.2.2.2 Secondary Analysis of Objective 2

As above, it is expected that some of the patients who initiate treatment in PROUD intervention clinics have been diagnosed with OUDs after randomization. It is also likely that patients may be newly attracted to the clinic (or to the health system entirely) specifically because of the PROUD intervention (based on the fact that at least 77% of patients treated in MA were new to the clinic after implementation).⁴⁷ The primary analysis of Objective 2 described above would miss any impact of the PROUD intervention on these patients, because they were not identified pre-randomization (because they were not previously diagnosed with OUDs or because they did not visit the clinic in the pre-randomization period). These secondary analyses are designed to capture these additional patients who may be affected by the PROUD intervention.

On the other hand, these secondary analyses must account for the fact that patients diagnosed with OUD post-randomization in the PROUD intervention clinics are likely to differ markedly from patients diagnosed with OUD post-randomization in the UPC clinics. Further, it is likely that these patients could differ in ways that may be associated with acute care utilization. To address this, analyses will adjust for potential confounding factors that are associated with both (1) acute care utilization, and (2) differences in characteristics of patients who get diagnosed with OUDs in PROUD intervention clinics (as compared to UPC clinics) after randomization.

We will first conduct preliminary analyses to compare the characteristics of patients diagnosed with OUDs in PROUD intervention clinics and UPC clinics. Because individuals who were first diagnosed with OUD prior to randomization are expected to be comparable across PROUD

intervention and UPC clinics (due to the randomization), these comparisons will focus on patients who entered our analytic sample because they were first diagnosed with OUDs in the 2 years post-randomization. Preliminary analyses will seek to understand differences in demographic characteristics, comorbidity, and utilization patterns between patients not included in primary analyses of Objective 2, but diagnosed with OUDs in PROUD intervention clinics and UPC clinics after randomization, in order to identify covariates for these secondary analyses of Objective 2.

We plan to fit a similar mixed-effect Poisson regression model as in the primary Objective 2 analysis but that includes additional covariates that allow the treatment effect comparing the PROUD intervention clinics to UPC clinics to differ among patients who were newly identified as having an OUD diagnosis in the post-implementation period. Specifically, the model will be of the following form:

$$\log[E(y_{ijk})] = \alpha_0 + \alpha_1 \text{period}_{ijk} + (\beta_0 + \beta_1 * \text{period}_{ijk}) * \text{trt}_{ij} + \gamma * z_{ijk} + \theta_{ij}$$

where *period* is an indicator for the period when the patient had their first documented OUD (in the post-randomization study phase versus pre-randomization), and the other terms are defined as in the primary analysis. We will adjust for the same covariates (in *z*) as in our primary Objective 2 analysis described above, as well as any covariate found to differ between individuals diagnosed with OUDs after randomization in the PROUD intervention clinics as compared to the UPC clinics, as identified in our preliminary analyses described above.

We will evaluate our secondary Objective 2 hypothesis by testing the composite null hypothesis $H_0: \beta_0 = \beta_1 = 0$ versus the alternative hypothesis that at least one of β_0 or β_1 is non-zero by conducting a likelihood ratio test. Additionally, we will estimate the treatment effect separately among people identified in the pre-implementation period (β_0) and people who weren't diagnosed until the post-implementation period ($\beta_0 + \beta_1$). The coefficient β_1 is the difference in the treatment effect comparing patients identified post-randomization to those identified in the pre-randomization period. This could either reflect a true difference in the treatment effect, or, more likely, it could reflect unmeasured confounders (not included in *z*) that differ between patients newly diagnosed post-randomization versus those with prior diagnoses. We do not have a specific hypothesis regarding β_1 because new patients may be attracted to the clinic to receive the PROUD intervention, as seen in [name],^{1,47} and these patients may be sicker (or healthier) than patients identified pre-randomization, which could increase (or decrease) acute care utilization during the period after randomization. We are not powered to test for β_1 rather, this is an exploratory analysis that will generate hypotheses for testing in future studies.

11.3 Other Secondary Analyses

11.3.1 Representativeness of Randomized UPC Clinics for Usual PC in the 6 Sites

As above, the process of recruitment of sites for the PROUD trial suggested that we did not recruit typical PC clinics. We therefore plan to conduct analyses to compare the recruited (randomized) clinics from each site, to randomly selected PC clinics from the same health system, in the five health systems able to provide data from 4 other PC clinics. These patient level analyses compare patients seen in the randomized PC clinics (2 per site; total clinics =10) to those seen in the other PC clinics that were not included in the trial (4 per site, total clinics=20) in the 3 years prior to randomization. Characteristics to be compared will include the demographics and clinical characteristics of patients visiting the clinics (e.g., mental health diagnoses, substance use disorders diagnoses, medical diagnoses such as HCV⁷³ and HIV, and pain diagnoses, as well as our measure of increased risk for OUDs).

Additionally, we will evaluate whether, for each of the baseline measures of OUD care described above, there is a difference in the measure among randomized clinics compared to 4 non-randomized UPC clinics from the same site, adjusted for differences in patient demographics across the clinics. Specifically, we will fit a mixed effect Poisson regression model of the clinic-level outcome data (e.g., number of patients with an OUD diagnosis during the year prior to randomization). As in our primary outcome model, we will adjust for correlation of outcomes from the same site by including a site-specific random intercept. Specifically, we will consider models of the form

$$\log(E(y_j)) = \log(n) + \alpha + \beta * \text{randomized} + \gamma z + \theta_j,$$

where y_j denotes the clinic-level outcome (e.g., number of patients with an ICD for OUD during the year prior to randomization), $\log(n)$ denotes an offset for the number of patients who visited the clinic in the year prior to randomization (for the recognition and initiation measures; for the retention measure it corresponds to the number of patients who initiated OUD treatment), *randomized* is an indicator for whether the clinic was included in the trial, z is a vector of demographic covariates being adjusted for (e.g., proportion male, comorbidity rates), and θ_j is a random intercept for site j . The coefficient β corresponds to the adjusted relative rate of the outcome (e.g., recognition of OUD) comparing *randomized* versus non-*randomized* clinics across all sites.

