Inclusion of a HCS-specific random effect. The above model accounts for clustering of patients within clinics but does not account for the possibility of additional correlation of outcomes from patients within the same HCS beyond any within-clinic correlation. The reason for this is because analyses of Phase 1 data suggested that within-clinic correlation was considerably larger than within-HCS correlation (the random-effect variance was 0.00016 for HCS versus 0.055 for clinic from a model including random effects for both). Although including a random-effect term that is not truly needed should not impact parameter estimates, including a HCS-level random effect leads to inferential challenges. In particular, as above there has not been guidance on applying small-sample DF correction methods when there are random-effects at two levels (here 12 clinics nested within 6 HCSs). We therefore chose the clustering level that explained most of the correlation for primary Objective 2 analyses. As a sensitivity analysis, we plan to examine the impact of additionally including a HCS-level random effect on the treatment effect parameter and standard error estimate.

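### The comparison of trial with non-trial clinics in Protocol 11.3.1 has no clinic-level variance term, so the standard error of its rate ratio is too small

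*Protocol*

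**What the plan says.** Protocol 11.3.1 asks whether the recruited clinics are typical of their systems. It compares trial clinics ("2 per site; total clinics =10") with other clinics ("4 per site, total clinics=20") on the baseline measures of OUD care. The method is: "we will fit a mixed effect Poisson regression model of the clinic-level outcome data". The linear predictor has a log(n) offset, an intercept, an indicator for randomized clinics, a demographic covariate vector z and a site intercept. On the site term it says: "As in our primary outcome model, we will adjust for correlation of outcomes from the same site by including a site-specific random intercept". On the target it says: "The coefficient β corresponds to the adjusted relative rate of the outcome", for randomized against non-randomized clinics. It gives no clinic-level term, dispersion parameter, test, alpha or degrees of freedom.

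The primary outcome model in Protocol 11.2.1 has the same kind of site intercept ("This model allows for clinics to be correlated within a health care system") and also a Gaussian error term for each clinic. SAP 1.1 places the comparison with non-randomized clinics in separate analysis plans that are not among these documents.

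**The concern.** The clinic is the unit being compared, so the spread between clinics of the same site determines how precisely beta is known. A Gaussian model estimates that spread through its residual. A Poisson model fixes the residual variance at the mean, so with only a site intercept the within-site spread not explained by z is taken to be Poisson noise. If clinics of one system really differ in their underlying rates, the standard error of beta is too small.

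This analysis is the protocol's answer to its own worry that the recruited clinics are not usual (Protocol 6.4 and 10.2.1), and it feeds the first planned manuscript in Protocol Table 11. Ordinary variation between clinics could be published as evidence that trial clinics are atypical, with intervals that look more exact than they are.

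**Working it through.** **Plan's own figure.** None is stated for this analysis. As a calibration on the nearest stated figures, take the Objective 2 type I errors in SAP 6.2.2 at tau = 0.23. Maximum likelihood with 12 clinics and 10 df understates the variance by about 10/12. P(|t10| > 1.96 x sqrt(10/12)) = 0.104 (stated Wald 0.104). P(|t10| > 2.228 x sqrt(10/12)) = 0.069 (stated BW 0.070).

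**Do clinics within a system differ beyond Poisson noise?** Inputs are the Phase 1 OUD counts in SAP 6.2.1 (9/12, 63/39, 58/200, 100/49, 27/10, 388/290) and the clinic sizes in Protocol Table 2. The count table uses letters and Table 2 uses system names, so the matching is not disclosed.

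- System E: 200/58 = 3.45. The largest size ratio in Table 2 is 34,114/16,540 = 2.06. Even if it belonged to E in the most favourable direction, the rate ratio is 3.45/2.06 = 1.67. Then ln(1.67) = 0.514, SE = sqrt(1/58 + 1/200) = 0.149 and z = 3.4.
- All six pairs, no size adjustment: mean(d²)/2 = 0.285, where d is the log ratio of a pair. The mean Poisson variance (average of 1/count) is 0.036. The difference is 0.249, an SD of 0.50.
- The matching to Table 2 size ratios that explains most variation leaves 0.021, an SD of about 0.15.

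The working range is therefore an SD of 0.15 to 0.50, before z. For acute care, SAP 5.3 says "within-clinic correlation was considerably larger than within-HCS correlation" (variance 0.055 against 0.00016). That is another outcome, so it is supporting evidence only.

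**Size of the inflation.** Set beta = 0, with five sites of 2 + 4 equal-sized clinics. Mean counts per clinic (m) are 10.5, 51, 129, 74.5 and 339, from systems A, C, E, I and K. Leaving out J as the system with no non-randomized clinics is inferred from Table 2. There are no covariates, and a two-sided 5% level is assumed.

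The trial-clinic contrast has variance proportional to the sum of m under Poisson. With clinic log-rate SD tau it is about the sum of (m + tau² m²). The variance is thus understated by VIF = 1 + tau² x (sum of m²)/(sum of m) = 1 + tau² x 139,823.5/604 = 1 + 231.5 tau². Actual type I error is 2 x [1 - Phi(1.96/sqrt(VIF))].

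- tau = 0.15: VIF = 6.21, error 43%.
- tau = 0.50: VIF = 58.9, error 80%.

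Simulation (20,000 runs per cell, Poisson test conditional on site):

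| Counts | SD 0 | SD 0.15 | SD 0.50 |
|---|---|---|---|
| Three-year Phase 1 | 5% | 43% | 80% |
| One third (assumed one-year window) | 5% | 24% | 67% |
| One tenth (assumed) | 5% | 11% | 46% |
| One thirtieth (assumed) | 5% | 7% | 26% |

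The scaled-down rows are needed because 11.3.1 illustrates a one-year window while Protocol Table 9 uses two and three years, and because initiation and retention counts will be smaller. Fitting the actual site-intercept Poisson mixed model (300 runs per cell, three-year counts) gave 63% at SD 0.23 and 81% at SD 0.50, against 59% and 80% from the conditional test. The mean estimate of beta stayed within 0.02 of zero throughout.

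**Remedies in the same setting.**

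- Clinic log-rates with site effects and t on 30 - 5 - 1 = 24 df: about 4-5% in every cell.
- Poisson model with a clinic random intercept, fitted by maximum likelihood: theory 9.2% with a normal reference and 7.7% with t on 24 df; simulated 4-11% with t on 24 df (300 runs per cell).
- Quasi-Poisson scale factor with 24 df: roughly 10-16% at three-year counts, because counts are very unequal between sites.

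**The case against.** Several points on the other side are sound.

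- A reader might infer that the model tests whether all clinics in a site share one rate, instead of whether trial clinics differ from the rest. It does not. Protocol 11.3.1 defines beta as the trial against non-trial contrast, the test has one degree of freedom, and the estimate is centred. Equal clinic rates given z is an assumption behind the standard error, not the hypothesis.
- A reader might take one rejection rate as a property of the plan. The documents support no single figure. The rate depends on assumed SDs and counts, and no one-year counts are given. It is 5% if clinics vary only by Poisson noise, and z will absorb some of the variation.
- A reader might call the likeness drawn with the primary outcome model a misstatement. That sentence concerns the site intercept, which both models have. The clinic error is simply missing from the Poisson form.
- The protocol presents these as models to be considered, and the separate SAP may already include a clinic term. That cannot be checked here and does not correct the protocol's stated model.
- Protocol 11.3.1 sets no significance rule, Protocol 11.5 promises cautious reading of secondary outcomes, and the protocol already says its clinics are not typical. This softens the consequence, but caution does not widen an interval that is too narrow.

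**Conclusion.** The point holds as a standard-error problem in a secondary observational analysis. Objectives 1 and 2 are not affected. The Poisson model stated in Protocol 11.3.1 omits within-site clinic variation, and the documents' own Phase 1 counts show such variation before adjustment for z. For OUD recognition the type I error is about 43-80% at three-year counts and 24-67% at one third of those counts. At one tenth it is about 11-46%, and at one thirtieth about 7-26%. These ranges rest on within-site SDs of 0.15 to 0.50, equal clinic sizes within a site, no covariates and the inferred choice of five systems. The direction is firm whenever clinics vary beyond Poisson noise and z; the exact size is not.

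**What to change.** In Protocol 11.3.1, do one of the following:

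1. Analyse clinic log-rates with site effects and t degrees of freedom based on clinics (24 before covariates, one fewer for each covariate). State how zero counts are handled; the simulation added 0.5.
2. Keep the Poisson model, add a clinic-level random effect to the site intercept, and name a small-sample degrees-of-freedom method.

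Do not rely on a quasi-Poisson scale factor alone. Report the rate ratio with its 95% confidence interval. State the time window for each measure so that 11.3.1 and Table 9 agree. Carry the same model into the separate observational SAP, or confirm that it is already there.

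The cost is one model term and a sentence on degrees of freedom. Confidence intervals become wider, and no new data are needed.
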